### Supplementary estimands for concomitant treatments

It may be of interest to consider supplementary estimands that assess the effect of each intervention in patients who simultaneously receive one or more of the other interventions. This may be relevant if future clinical practice incorporates one or more of the study interventions as standard and the additional effect of the remaining intervention(s) needs to be considered.

#### Exploratory estimands: treatment combinations

Further estimands as set out in Supplementary Table D will enable exploration of the combined effect of the interventions compared to standard of care in the event that each intervention in isolation shows no benefit.

Analysis population: We will use an Intention to Treat principle. Analyses will include all randomised participants in the arm they are allocated to regardless of the intervention received or intervention discontinuation but will exclude participants who are lost to follow-up with no data on the primary outcome at day 90, as no multiple imputation will be performed for the primary analysis. It is anticipated that >98% of all patients will have primary outcome data at day 90 and therefore there will be no substantial violation of the Intention to Treat principle. We expect that in this analysis population it will be possible to account for all participants' clinical status over time for the study

Sponsor: Imperial College London

Version 1.1 22-Aug-2023

duration up to day 90, and reasonable to assume discharged status if no mortality or inpatient record can be identified via data linkage; therefore no missing primary outcome data is expected.

**Analysis model:** A single factorial model will be used to simultaneously estimate the estimands for the diagnostic and fluid interventions in the full study population, and will also include GM-CSF treatment status as a covariate, as this approach results in unbiased marginal odds ratios for the primary estimands.(49) A second factorial model, using data only for the subjects eligible for GM-CSF, will be used to estimate the estimands for the GM-CSF trial, and will include the other interventions as covariates.

In both cases, in order to estimate the difference due to the intervention effect over time we will fit a longitudinal Proportional Odds model. This will provide the between arm proportional Odds Ratio of moving from one clinical state to a better clinical state averaged over the 90 days follow-up period. We will also use the models to estimate the between-arm proportional Odds Ratio of moving to a better clinical state on Day 90, and the 90-day mortality Odds Ratio between intervention arms. Terms for interactions between timepoints and treatment will be included. The models will have a random intercept for each subject and will adjust for covariates including age and the variables used for minimisation.

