# **Procedures for Withdrawal from Study**

Patients will be free to withdraw at any time. If the patient (or their personal/professional legal representative) wishes to withdraw from the study during the treatment period the treating physician will no longer follow the trial protocol and the study drug will be stopped. If the participant withdraws from the study this will be documented in the eCRF and medical records.

The patient will be able to either withdraw completely from the trial or from certain elements. Further follow-up visits as part of the clinical trial will cease. However, the participant will be asked if data collection through data linkage of routinely collected data, including long-term follow-up can continue.

Participants will be asked if previously collected, stored blood samples can be used for further analyses or if they would prefer their samples to be destroyed.

Already collected data will not be deleted as these will include important safety information which would be processed as part of a legitimate interest.

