#### Statistical analysis

#### Overview

We will undertake both a frequentist and Bayesian analysis on the primary outcome and a frequentist analysis on all secondary outcomes. For the primary outcome no multiple imputation will be used for missing outcome data as it is anticipated missing data will be extremely low due to the ability to retrieve information from routinely collected clinical data within medical records. The Bayesian analysis on the primary outcome will be used to facilitate interpretation and we will use vague prior distributions on the model parameters including the treatment effect parameter. In the frequentist approach we will report the Summary statistic (e.g. Odds Ratio) with 95% confidence intervals and the interpretation will focus on the magnitude of the intervention effect and precision of this estimate. In the Bayesian analysis we will report the probability of superiority, and the probability of superiority by a meaningful margin which will be pre-specified in the statistical analysis plan after consultation with Patient and Public Involvement and Engagement (PPIE) members and clinical teams.

For secondary outcomes where missing outcome data is greater than approximately 5% we will undertake multiple imputation and the model will be specified in the statistical analysis plan and will include the outcome as well as stratification variables.

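### The primary analysis drops participants with no day-90 outcome because nothing is imputed, although its longitudinal model can use their earlier states without imputation

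*Protocol*

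**What the plan says.** All of the following is in the protocol.

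- **Exclusion.** The Analysis population paragraph in section 9 adopts Intention to Treat, then "will exclude participants who are lost to follow-up with no data on the primary outcome at day 90". It justifies this by the absence of imputation, which the Overview of the statistical analysis also states: "For the primary outcome no multiple imputation will be used for missing outcome data". It adds: "It is anticipated that >98% of all patients will have primary outcome data at day 90".
- **Coding.** For the participants who remain, the same paragraph finds it "reasonable to assume discharged status if no mortality or inpatient record can be identified via data linkage", and concludes: "therefore no missing primary outcome data is expected". In the sample size section, discharged is state 1, the best of the four, and death is state 4 and absorbing.
- **Model.** The Analysis model paragraph fits a longitudinal proportional odds model to the four states: "The models will have a random intercept for each subject and will adjust for covariates including age and the variables used for minimisation". Its main result is an odds ratio for "moving from one clinical state to a better clinical state averaged over the 90 days follow-up period".
- **Data.** The Visit Schedule in section 6 has daily clinical data in ICU to day 28, final hospital data up to day 90, and vital status at day 90. On withdrawal, section 7 says: "Already collected data will not be deleted as these will include important safety information". Continued linkage is a separate question put to the person who withdraws.
- **Sensitivity.** The section on estimand definitions promises a sensitivity analysis of the statistical assumptions. The section listing sensitivity analyses names multiarm models and alternatives to proportional odds. It names nothing on missing states or on the assumed-discharged rule.

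**The concern.** The exclusion is presented as a consequence of not imputing, but it is not one. A likelihood-based model with a random intercept takes each participant's observed states as they come and does not need the last one. Requiring a day-90 value turns a repeated-measures analysis into a completers analysis. That discards ICU and hospital states which bear directly on an odds ratio averaged over 90 days. It also swaps a missing-at-random assumption, conditional on the observed states, for the stronger one that those dropped resemble those kept.

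The exclusion is also related to outcome by construction. Anyone with a recorded death has a known state at day 90, so only people last known alive can be dropped. If more are dropped in one arm, that arm's observed mortality rises relative to the other with no treatment effect behind it. The diagnostic and fluid trials are open-label, so such a difference cannot be excluded, though the protocol gives no figure for it.

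A smaller point concerns the assumed-discharged rule. The text does not say what happens to a participant whose linkage was refused or failed, so the boundary between exclusion and coding as discharged is left open.

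**Working it through.** **Inputs.** From the sample size section: 30% versus 25% mortality, two-sided 5%, 90% power, 1674 per arm, 10% inflation for interaction, 2% for loss. The GM-CSF trial has 1300 participants, 45% mortality, a 9-point difference and about 2% loss. From Table 2, control arm: day-90 probabilities 0.60, 0.05, 0.05 and 0.30 for states 1 to 4, and mortality of 0.27 at day 28. Loss and linkage failure by arm are not in the protocol; the values below are assumptions.

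**1. The plan's own size.** The pooled two-proportion formula without continuity correction gives 1674 per arm. Then 2 × 1674 × 1.10 / 0.98 = 3757.96, so 3758 is reproduced. For GM-CSF the formula gives 624 per arm, and 2 × 624 / 0.98 = 1274. With 98% of 1300 analysed, power is 0.906, which agrees with the stated 90%.

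**2. How many are dropped.** 0.02 × 3758 = 75; 0.02 × 1300 = 26.

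**3. What keeping them does to power.** For 30% versus 25%, ignoring the interaction allowance, power is 0.925 with 98% of 3758 analysed and 0.930 with all. No sample-size figure changes.

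**4. Effect of the exclusion on mortality.** If a share e of an arm is excluded and all are survivors, observed mortality is m / (1 − e).

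- Balanced, no true effect, e = 0.02 in both arms: 0.30 / 0.98 in each arm, difference 0.
- Balanced, true 5-point effect: 0.30 / 0.98 − 0.25 / 0.98 = 0.306 − 0.255 = 0.051, practically unchanged.
- Unbalanced, no true effect, e = 0.01 versus 0.03: 0.30 / 0.97 − 0.30 / 0.99 = 0.309 − 0.303 = 0.006, or 0.6 points.
- Outer limit, 2% lost per arm, all of them in fact dead in one arm and none in the other: 0.02 × (1 − 0) = 2 points. Nothing suggests a pattern of that kind.

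**5. Effect of the discharged rule if it were applied to unlinked people.** Let a share of each arm be recoded to state 1, with their true states following Table 2 and no treatment effect. A day-90 proportional odds fit has standard error √(12 / (3758 × (1 − Σp³))) = √(12 / (3758 × 0.757)) = 0.065 for the log odds ratio.

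| Unlinked, control vs intervention | Odds ratio | Type I error |
|---|---|---|
| 2% vs 2% | 1.00 | 5.0% |
| 0% vs 1% | 1.016 | 5.7% |
| 0% vs 2% | 1.032 | 7.8% |

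With a true effect as in scenario 4 of Table 3 (day-90 odds ratio 1.147), 2% unlinked in both arms dilutes it only to 1.145. These figures use day 90 alone rather than the longitudinal model. They also lean high, because they give unlinked people the full 30% mortality although in-hospital deaths are recorded directly.

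**The case against.** The protocol states its departure from Intention to Treat openly and expects it to affect under 2%. Vital status is scheduled at day 90, so linkage is not the only source. A person may withdraw and still allow linkage. The steering committee monitors follow-up to day 90 and the completeness of the clinical states. A sensitivity analysis of statistical assumptions is promised, and its detail may properly sit in the statistical analysis plan. All of this stands, and it keeps the point small. It does not rescue the reason given for the exclusion, which the protocol itself fixes.

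Three stronger readings are tempting, and the protocol does not support them.

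- **That the two rules contradict each other.** Read in order, the exclusion comes first, and the expectation of no missing data describes those who remain. The boundary needs clearer wording; that is all.
- **That the discharged rule hides 0.6 points of mortality (0.02 × 0.30).** The rule speaks of finding no record through linkage, which presupposes that linkage was done, so someone who refused it fits the exclusion better. Index-hospital deaths are captured directly, and Table 2 puts 27 of the 30 points of mortality by day 28. If mortality among such people were 5%, an assumed value, the figure would be 0.02 × 0.05 = 0.1 point. It would also be a shift within one arm, which cannot be set against a between-arm difference.
- **That withdrawal after deferred consent will differ by arm.** The consent process makes withdrawal by survivors possible, but nothing in the protocol indicates a difference between arms. It is least plausible in the double-blind GM-CSF trial.

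**Conclusion.** The point holds as a minor one. The stated ground for excluding participants without day-90 data is wrong for the model chosen, and the rule discards states that are collected and retained and can remove only people last known alive. At 2% loss or less, bias is near zero when loss is balanced. The 0.6-point illustration rests entirely on an assumed 1% versus 3% split with every excluded person a survivor. It shows when the rule would matter and is not a forecast. Keeping these participants relies on their later states being missing at random given the observed states and covariates, which is weaker than what complete-case exclusion needs. The sample size is unaffected.

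**What to change.** In the Analysis population paragraph:

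1. Replace the exclusion with a rule that every randomised participant with at least one observed post-randomisation state enters the primary model with all observed states. Report by arm how many have no day-90 state and how many have no state at all.
2. State that discharged is assumed only where linkage to national records, or day-90 vital status, was obtained and no death or inpatient stay was found. Treat participants whose linkage was refused or failed as missing after their last known state.
3. Name both assumptions in the sensitivity analysis that the estimand section promises, for example with best-case and worst-case states for the missing period.

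The cost is a change of wording and a linkage-status flag in the dataset. The model and the sample size stay as they are, and the data to be collected stay the same apart from that flag. The change should be settled before outcome data are seen.

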#### Randomisation and Blinding

Participants will be allocated to interventions using minimisation with a 20% random element.(41) Allocation to the first two interventions (diagnostic and fluid trials) will occur concurrently. Participants who are sicker on admission or deteriorate will be eligible to be allocated to the third intervention (GM-CSF trial). The following variables will be used for minimisation:

- Diagnostic trial: centre, vasopressor use (Y/N), source of infection (community vs hospital acquired)
- Fluid trial: centre, respiratory support (Y/N), vasopressor use (Y/N)
- GM-CSF trial: Centre, allocation in Diagnostic and Fluid trials, source of infection (community vs hospital acquired)

Concealment will be achieved through use of an online system; however, the diagnostic and fluid trials are open-label whereby participants, the clinical team and study team will not be masked to the interventions. No aggregated data by arm will be available to the study team throughout the trial.

The GM-CSF trial will be double-blind whereby the participants, clinical team, and study team will be masked to treatment allocation. This will be achieved by providing GM-CSF and matching placebo (supplied and imported from the USA by Partner Therapeutics) in similar vials and then masked by over-labelling the vials and packaging in individual numbered patient packs.

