# **Visit Schedule**

Visit	Day 0 (pre randomisation)	Day 1 (post- randomisation)	Day 2	Day 3-5	Day 6-12	Day 12-28	Day 90	Day 180	Day 365
Screening	X	randomicationy							
Informed Consent (Patient consent/ PerLR/ ProLR / Retrospective Patient Information & consent)		Patient / PerLR / ProLR will be obtained initially. Retrospective patient consent will be obtained when the patient has recovered capacity to consent.							
Inclusion / Exclusion criteria	Х								
Randomisation to diagnostic & fluid trials	Х								
Randomisation to GM-CSF trial	_	Anytime up to 5 days (120 hours) after ICU admission once meets additional inclusion / exclusion criteria							
PCR & PCT test if in relevant arm of diagnostic trial.		X PCT only on Day 2							
Conservative fluid management & de-resuscitation if in relevant arm of fluid trial		Х	Х	X					
Study drug (GM-CSF / placebo) administration		For 8 d	ı lays after raı	ndomisatio	on				

Sponsor: Imperial College London

Version 1.1 22-Aug-2023

Research blood samples for all patients		X	Additional samples if in GM-CSF trial						
Data Collection / Follow up									
Baseline data	Х	Х							
Daily collection of clinical data up to Day 28 while in ICU		Х	Х	х	Х	Х			
Final hospital data collection on discharge from hospital (up to Day 90 max)							х		
Day-90 vital status							Х		
EQ-5D-5L & MOCA-Blind. (Final contact with patient)								Х	
1 year vital status (through data linkage only)									Х
Final Visit									Х

Sponsor: Imperial College London

Version 1.1 22-Aug-2023

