#### 9. STATISTICAL ANALYSES

### Sample Size and power considerations

The sample size has been calculated based on 90-day mortality. To increase the power of the trial the primary outcome will include both 90-day mortality and clinical state (in-hospital without organ support, in-ICU with organ support, discharged) over 90 days. Simulations to further examine the power of the study under a range of conservative outcomes on the primary outcome with clinical state included have been performed on the planned trial sample size based on mortality alone.

The initial calculation used data from the ICNARC Case Mix Programme which reported a mortality rate of 31.8% for all sepsis admissions to ICU.(43) Allowing for the trial exclusion criteria we anticipate a 30% mortality rate in the standard of care arm.

In the diagnostic and fluid trials we aim to recruit 3758 patients to both trials. This is based on a clinically important target difference in mortality of 5%. Assuming 30% mortality, 5% reduction, 90% power, 5% two-sided type I error we will require 1674 per arm. We then inflate by 10% for a potential interaction effect between the intervention arms, and 2% to account for loss to follow-up.

The high-risk subset (35% eligibility for GM-CSF) will have a higher control mortality rate.(43-45) We assume a 45% mortality rate in the standard of care arm. Our meta-analysis for GM-CSF in sepsis trials demonstrated a relative risk for mortality of 0.74 (95%CI 0.49-1.14). We aim to recruit 1300 participants which will provide 90% power to detect 9% difference in mortality with type I two-sided error or 5%, and factoring in approximately 2% loss to follow up.

No adjustments for multiple comparisons have been made for these three trials as the comparisons are three distinct treatments where each result will provide a separate conclusion. (46)

In addition, we have undertaken simulations to further examine the power of the primary analysis of 90-day mortality and clinical states (in-hospital without organ support, in-hospital with organ support, discharged) for the antibiotic and fluid trials, assuming a more conservative reduction in mortality. Treating clinical state as an ordinal outcome which is repeatably observed over time increases statistical efficacy because it makes the most of all the information available. We define clinical status as an ordinal outcome with three passing states and one absorbing state.

Clinical status is categorised as:

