1. Discharged from hospital

Sponsor: Imperial College London

Version 1.1 22-Aug-2023

- 2. In-hospital without Organ Support
- 3. In-ICU with Organ Support
- 4. Death (absorbing state i.e. cannot transition out of this state)

Using data from the VANISH and LeoPARDS trials (44, 47) we estimated the proportion in each clinical state on days 0, 7, 14, 28 and 90 days in the standard of care arm (Table 2).

Sponsor: Imperial College London

Version 1.1 22-Aug-2023

Table 2: The anticipated probability of each clinical state over the first 90 days in the standard of care arm

State	0	7	14	28	90
1 = Discharge	0.00	0.06	0.21	0.42	0.60
2 = Hospital without support	0.15	0.48	0.32	0.17	0.05
3 = ICU with support	0.85	0.41	0.29	0.14	0.05
4 = Death	0.00	0.05	0.18	0.27	0.30

Simulations then estimated power for the new treatment under five scenarios, under which mortality reduction in the treatment arm was always kept at 3%, whereas the proportion transitioning to a better (lower) clinical state changed in each scenario, as shown in Table 3. Data for each simulation was generated using a Markov transition model. First, at least two sets of State Transition Probabilities (STP) corresponding to each timepoint and each scenario were estimated, using iterative methods to minimise the difference between the target clinical state probabilities and those derived from the STPs. Then, for each set of STPs, random draws of a standard (0,1) uniform distribution for each individual and timepoint were mapped onto the discrete clinical states by partitioning the interval [0,1] into sub-intervals with widths corresponding to the STPs. These simulations were analysed using a mixed effects proportional odds model which included the discrete timepoints, binary treatment variable and interactions between them as fixed effects, and participant as a random effect. In total 300 simulations were analysed for each scenario. The power was calculated based on the proportion of simulations from a two-sided hypothesis where the 95% confidence interval excluded the value of no difference (i.e. OR = 1).

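### The primary diagnostic and fluid model adjusts for GM-CSF status, which is set after those randomisations, so its odds ratios cannot be called unbiased and can err in either direction if an intervention changes GM-CSF entry

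*Protocol*

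**What the plan says.** Protocol section 9, under Analysis model, specifies one factorial model in the full study population for the diagnostic and fluid interventions. It "will also include GM-CSF treatment status as a covariate, as this approach results in unbiased marginal odds ratios for the primary estimands".

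Other parts of the protocol fix when that status arises:

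- Diagnostic and fluid allocations are made together, and patients more than 24 hours past ICU admission are excluded from them (sections 5 and 6).
- On the third allocation, Randomisation and Blinding says: "Participants who are sicker on admission or deteriorate will be eligible to be allocated to the third intervention (GM-CSF trial").
- The Visit Schedule puts that allocation at "Anytime up to 5 days (120 hours) after ICU admission once meets additional inclusion / exclusion criteria".
- The additional GM-CSF inclusion criteria require ventilation or two-organ support, plus low lymphocyte counts on two consecutive days. They may be met after initial trial entry.
- GM-CSF allocation is minimised on the diagnostic and fluid allocations, so it follows them.

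Appendix 2, Supplementary Tables A and B, sets a treatment-policy strategy for receipt of the other trial interventions in the primary estimand. It defines the odds ratio as conditional on age and the minimisation variables. GM-CSF status is not among them.

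The one sensitivity analysis that the protocol commits to relaxes the no-interaction assumption. All secondary-outcome models take the same adjusting variables as the primary analysis.

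**The concern.** In an ordinary factorial trial the other factor is randomised in everyone at baseline, and adjusting for it is harmless. Here the covariate carries two things. One is the GM-CSF versus placebo contrast, which is randomised among entrants. The other is whether the patient entered the GM-CSF trial at all, which is decided after the diagnostic and fluid allocations. The second part is the problem. It reflects severity, and organ support is also a state of the primary outcome.

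If either strategy changes who needs organ support or who survives to qualify, conditioning on entry blocks part of the total effect and compares groups that randomisation no longer balances. The diagnostic and fluid trials are open-label, so the decision to enrol in the GM-CSF trial could also differ by known arm.

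At stake are the primary estimates of two comparisons of 3758 patients. The covariate also carries into secondary outcomes such as the durations of ventilation, vasopressor use and renal replacement, which lie close to the entry criteria.

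**Working it through.** **Inputs from the protocol (section 9, Sample Size and power considerations).** For the diagnostic and fluid trials: "Assuming 30% mortality, 5% reduction, 90% power, 5% two-sided type I error we will require 1674 per arm". The total is then raised by 10% for interaction between arms and by 2% for attrition. About 35% of participants are expected to qualify for GM-CSF, with control mortality among them taken as 45%. The power simulations use a smaller mortality effect of 3 points.

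**The plan's own figure.** n per arm = [1.960 × √(2 × 0.275 × 0.725) + 1.2816 × √(0.30 × 0.70 + 0.25 × 0.75)]² / 0.05² = 1674. Then 2 × 1674 × 1.10 / 0.98 = 3758. Both reproduce.

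**Mortality outside the GM-CSF subset.** (0.30 − 0.35 × 0.45) / 0.65 = 0.219.

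**Assumptions.** The protocol gives no effect of either strategy on GM-CSF entry, so entry in the intervention arm is varied by assumption against 35% in control. GM-CSF itself is taken as null. A common odds ratio θ applies within the entered and not-entered strata. It is solved so that total intervention-arm mortality is 27% (3-point effect) or 25% (5-point effect).

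**Total effect without the covariate.**
- 3 points: (0.27/0.73) / (0.30/0.70) = 0.863, log −0.147.
- 5 points: (0.25/0.75) / (0.30/0.70) = 0.778, log −0.251.

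**With the covariate.** The protocol does not say how status is coded. Under three-level coding (not entered / placebo / GM-CSF) the model returns θ. Example with entry at 31% and a 3-point effect:
- θ = 0.897.
- Entered: odds 0.818 × 0.897 = 0.734, risk 0.423.
- Not entered: odds 0.281 × 0.897 = 0.252, risk 0.201.
- Total: 0.31 × 0.423 + 0.69 × 0.201 = 0.270, as required.
- Log θ = −0.109, and 0.109/0.147 = 74%, so 26% of the total log odds ratio is removed.

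Two-level coding (GM-CSF / not) was fitted by logistic regression on expected cell counts with N = 3758. Each cell shows the adjusted odds ratio and the share of the total log odds ratio removed.

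| Entry, intervention arm | 3-point, three-level | 3-point, two-level | 5-point, three-level | 5-point, two-level |
|---|---|---|---|---|
| 35% (no change) | 0.855, none | 0.860, none | 0.766, none | 0.773, none |
| 33% | 0.876, 10% | 0.868, 4% | 0.785, 4% | 0.780, 1% |
| 31% | 0.897, 26% | 0.876, 10% | 0.804, 13% | 0.788, 5% |
| 29% | 0.919, 42% | 0.884, 17% | 0.823, 23% | 0.795, 9% |

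The first row differs from 0.863 and 0.778 only through non-collapsibility: the log odds ratio is about 106% of the total value with three levels and 102% with two.

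**Direction.** If entry instead rises to 37% under a true 3-point effect, three-level θ = 0.836. Check: entered odds 0.818 × 0.836 = 0.684, risk 0.406; not-entered odds 0.281 × 0.836 = 0.235, risk 0.190; 0.37 × 0.406 + 0.63 × 0.190 = 0.270. The log is −0.179, or 122% of the total effect, so the benefit is exaggerated.

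**Null case.** If mortality is 30% in both arms but entry falls to 30%, the adjusted odds ratio is about 1.06 with three levels (two-sided rejection about 12–14% instead of 5%) and about 1.02 with two levels (about 6%).

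**The case against.** The strongest defence is that entry may hardly move. Some patients qualify on severity at admission, and Table 2 puts 85% in ICU with organ support on day 0. The second procalcitonin comes 18–36 hours after the first, de-resuscitation is assessed on days 2–5, and GM-CSF entry closes at 120 hours. This stands as a limit on size: the shifts used here are assumptions, and with unchanged entry nothing is lost. It does not rescue an unconditional claim of unbiasedness, because that claim needs neither strategy to affect organ support or survival, which is part of what the trial tests.

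A second defence is that adjusting for a co-intervention does not in itself breach treatment policy. That is right. The breach comes from conditioning on post-randomisation entry. The plainest textual conflict is with Appendix 2, which lists the conditioning variables without GM-CSF status and describes a conditional odds ratio where the analysis section says marginal.

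Third, omitting the covariate lets in-trial GM-CSF use pass into the comparison. That is what treatment policy asks for, and it is small. With GM-CSF lowering mortality by 9 points and entry 5 points lower, the contribution is 0.05 × 0.5 × 0.09 = 0.2 percentage points.

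Two stronger readings are tempting. A reader might infer that the model always removes part of the effect. The protocol does not show that entry changes, and the direction is not fixed. A reader might also infer that it turns benefit into apparent harm. Suppose 4% are kept out of the GM-CSF trial and die at 30% instead of 45%. Total mortality falls by 0.04 × 0.15 = 0.6 points (log odds ratio −0.029). Mortality among the not-entered rises from 0.219 to (0.65 × 0.219 + 0.04 × 0.30) / 0.69 = 0.224, a log odds ratio of +0.03. That is one stratum, not the model's coefficient. The pooled adjusted log odds ratio is +0.016 (SE 0.074) with three levels and −0.011 with two, so it is indistinguishable from no effect.

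**Conclusion.** Wrong as written. The covariate is fixed after the diagnostic and fluid randomisations and depends partly on their possible consequences. The sentence claiming unbiased marginal odds ratios cannot stand, and the model does not match the estimand in Appendix 2. No planned analysis would reveal a bias, because the protocol commits to no model without the covariate.

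The size is uncertain. Over assumed falls in entry of 2 to 6 points, the loss ranges from 1% of the log odds ratio (5-point effect, two-level coding) to 42% (3-point effect, three-level coding). It is zero if entry is balanced and reverses if entry rises. The calculation uses the protocol's 30%, 35% and 45% on 90-day mortality, a null GM-CSF effect and a common within-stratum odds ratio. It does not reproduce the longitudinal ordinal model with a subject random intercept. The separate GM-CSF model is not affected, since the covariates it takes from the other trials were allocated earlier.

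**What to change.** Remove GM-CSF status from the primary diagnostic and fluid model and from the matching secondary-outcome models. Keep the two randomised factors, age and the minimisation variables. Delete the justification about unbiased marginal odds ratios, so that the text agrees with Appendix 2. Keep the GM-CSF-adjusted model as a labelled sensitivity analysis with the coding of status defined, and report GM-CSF entry by diagnostic and fluid arm so that readers can see whether it shifted.

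Omitting the covariate cannot confound effects that were randomised earlier. The cost is a short text change in the protocol, carried into the SAP. No new data are needed and N stays at 3758.
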